4.5 TERTIARY/EXPLORATORY ENDPOINT(S) ANALYSIS

4.5.1 Definition of endpoints

The following tertiary/exploratory efficacy endpoints will be explored in the Phase 2 portion of the study:

Term	Percentage
GMOs	85%
Organic	95%
Natural	95%
Artificial	65%
Organic	85%
Natural	85%
Artificial	75%
Organic	85%
Natural	85%
Artificial	75%

4.5.2 Main analytical approach

4.6 MULTIPLICITY ISSUES

No multiplicity issues are anticipated in this study.

4.7 SAFETY ANALYSES

For the Phase 1 portion of the study, pre-defined unacceptable toxicities) will be listed by participant using the Safety-evaluable Phase 1 population defined in [Section 3](#).

All safety analyses detailed below will be performed on the All Treated population as defined in [Section 3](#), unless otherwise specified, using the following common rules:

- The analysis of the safety variables will be essentially descriptive, and no testing is planned.
- Safety data in participants who do not belong in the All treated (eg, treated but not enrolled) will be provided.

4.7.1 Extent of exposure

4.7.1.1 *Overall exposure*

The dose information will be assessed by the following variables:

- Overall number of cycles started, defined by the number of cycles in which at least one dose of any study interventions is administered.
- Duration of IMP exposure (in weeks) is defined as $[(\text{last date of IMP administration}) - (\text{first date of IMP administration})] / 7$.

- The first day of IMP administration is defined as the first administration date with non-zero dose for the IMP. The last date of IMP administration is defined as follows:
 - date of the last IMP dose + 7 if the last cycle is a QW cycle or date of death + 1, whichever is earlier
 - date of the last IMP dose + 14 if the last cycle is a Q2W cycle or date of death + 1, whichever is earlier

The total number of cycles started, number of cycles started by participants will be summarized as a quantitative variable and by category (number (%)) of participants receiving 1 cycle, 2 cycles, 3 cycles). The duration of overall exposure will be summarized quantitatively.

The following variables will be computed to describe overall dose modification (cycle delay):

- Cycle delay: A cycle is deemed as delayed if the (start date of the current cycle – start date of the previous cycle) – duration of a cycle (ie, 28) is >2 days. Cycle delay is not defined for the first cycle.

Cycle delay will be analyzed at the participant (with number of participants used as denominator) and cycle (with number of cycles used as denominator) levels, as follows:

- Number (%) of participants with a least 1 cycle delayed
 - Number (%) of participants with a cycle delayed between 3 and 7 days (using maximum delay across all cycles)
 - Number (%) of participants with a cycle delayed between 8 and 14 days (using maximum delay across all cycles)
 - Number (%) of participants with a cycle delayed >14 days (using maximum delay across all cycles)
- Number (%) of cycles delayed
 - Number (%) of cycles delayed between 3 and 7 days
 - Number (%) of cycles delayed between 8 and 14 days
 - Number (%) of cycles delayed >14 days
- Dose delay: within a cycle, the treatment window is ± 1 day for each of the weekly administrations and ± 2 days for each of the Q2W administrations. Within a cycle, a dose is deemed to have been delayed if the treatment is ≥ 2 days beyond the theoretical day of treatment for weekly dose, or ≥ 3 days beyond the theoretical day of treatment for Q2W dose.

4.7.1.2 IMP exposure

The dose information will be assessed by the following:

- Total number of cycles started
- Number of cycles started per participant

- Duration of IMP exposure (in weeks) is defined as [(last date of IMP administration) – (first date of IMP administration)] / 7.
- The first day of IMP administration is defined as the first administration date with non-zero dose for the IMP. The last date of IMP administration is defined as follows:
 - date of the last IMP dose + 7 if the last cycle is a QW cycle or date of death + 1, whichever is earlier
 - date of the last IMP dose + 14 if the last cycle is a Q2W cycle or date of death + 1, whichever is earlier
- Actual dose (mg/kg): is defined as the actual dose (mg) administered divided by the body weight at the time
- Cumulative dose (mg/kg): the cumulative dose is the sum of all actual doses (mg/kg) of IMP, given from first to last administration
- Actual dose intensity (ADI [mg/kg/week]): defined as the cumulative dose (mg/kg) divided by the duration of IMP exposure (weeks)
- Planned dose intensity (PDI [mg/kg/week]): corresponds to the planned dose (mg/kg) multiplied by the theoretical total number of doses started and divided by the theoretical cycle duration expressed in weeks (ie, 4 weeks per cycle started)
- Relative dose intensity (RDI, in %): $100 \times \frac{\text{ADI (mg/kg/week)}}{\text{PDI (mg/kg/week)}}$

The total number of doses, total number of cycles started, number of cycles started by participant will be summarized as a quantitative variable and by category (number [%] of participants receiving 1 cycle, 2 cycles, 3 cycles). Duration of IMP exposure, cumulative dose, ADI and RDI will be summarized quantitatively.

The following variables will be derived to describe dose modifications:

- Dose reduction: The first IMP administration will not be counted as a dose reduction. For the second and subsequent IMP administrations, dose reduction will be determined using the dose level intervals provided in [Table 4](#), by comparing the current dose level to the previous dose level. If the current dose level is below the dose level interval of the previous dose administration, then the current dose level is considered reduced.

Table 4 - IMP dose reduction criteria

Actual dose level	Dose level interval
Starting dose (10 mg/kg)	>7.5 mg/kg
Dose level -1 (5 mg/kg)	>0 mg/kg and \leq 7.5 mg/kg

- Dose omission is defined as a dose not administered at the scheduled visit but administered afterwards.
- Dose interruption: A dose will be considered as interrupted if the IMP administration is stopped during an infusion regardless of whether it is restarted or not.

Dose modifications will be analyzed by participant and cycle as follows:

- **Participant** (number of participants treated will be used as denominator)
 - Number (%) of participants with at least 1 dose delayed
 - Number (%) of participants with at least 1 dose modification
 - Number (%) of participants with at least 1 dose reduction
 - Number (%) of participants with at least 1 dose omission
 - Number (%) of participants with at least 1 dose interruption
- **Cycle** (number of cycles started will be used as denominator)
 - Number (%) of cycles with at least 1 dose delayed
 - Number (%) of cycles with at least 1 dose modification
 - Number (%) of cycles with at least 1 dose reduction
 - Number (%) of cycles with at least 1 dose omission
 - Number (%) of cycles with at least 1 dose interruption

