6.1 STUDY INTERVENTION(S) ADMINISTERED

Table 3 - Overview of study interventions administered

Intervention name	Isatuximab	Premedications (see description after this table for NIMP)
Type	Drug	See description after this table for NIMP
Dose formulation	Concentrated solution for infusion	See description after this table for NIMP
Unit dose strength(s)	20 mg/mL (500 mg/25 mL) isatuximab in 20 mM histidine, 10% (w/v) sucrose, 0.02% (w/v) polysorbate 80, pH 6.0	See description after this table for NIMP
Dosage level(s)	See Table 4 for details on the dose levels and schedule	See description after this table for NIMP
Route of administration	IV infusion See below for rate and duration of infusion	See description after this table for NIMP
IMP and NIMP	IMP	NIMP
Packaging and labeling	Isatuximab will be provided in 1 glass vial per box. Each vial and box will be labeled as required per country requirement	Each treatment container will dependent on country sourcing. Each container will be labeled as required per country requirement

Abbreviations: IMP = investigational medicinal product, IV = intravenous, NIMP = noninvestigational medicinal product.

Between the protocol-scheduled on-site visits, interim visits may be required for IMP dispensing. As an alternative to these visits, isatuximab may be supplied from the site to the participant via a Sponsor-approved courier company where allowed by local regulations and approved by the participant.

Starting dose of investigational medicinal product (isatuximab) and de-escalation design

The SD of IMP is 10 mg/kg QW for 4 weeks followed by Q2W. If the SD is determined not to be sufficiently well-tolerated, 6 additional (minimum) safety evaluable participants will be enrolled at DL-1 (ie, 5 mg/kg QW for 4 weeks followed by Q2W) (see [Table 4](#) for details on the dose levels and schedule for Phase 1).

Overall safety monitoring will also be performed throughout the conduct of the study.

Table 4 - Dose level and schedule in Phase 1

Dose Level	Isatuximab 1 cycle = 4 weeks (28 days)
SD	10 mg/kg QW × 4 for Cycle 1 → Q2W for cycles 2 and 3
DL-1	5 mg/kg QW × 4 for Cycle 1 → Q2W for Cycles 2 and 3

Abbreviations: DL-1 = dose level minus 1, QW = once weekly, Q2W = once every 2 weeks, SD = starting dose

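### SAP 4.7.1.2: final doses lost by stopping early on schedule never lower relative dose intensity, and the dose-omission definition describes a late dose rather than a skipped one

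*SAP*

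**What the plan says.** The schedule in Protocol 6.1 is "10 mg/kg QW × 4 for Cycle 1 → Q2W for cycles 2 and 3", with "1 cycle = 4 weeks (28 days").

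SAP 4.7.1.2 derives three intensity measures.

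- Actual dose intensity (ADI): "Actual dose intensity (ADI [mg/kg/week]): defined as the cumulative dose (mg/kg) divided by the duration of IMP exposure (weeks"). The exposure period closes at "date of the last IMP dose + 7 if the last cycle is a QW cycle or date of death + 1, whichever is earlier", or at "date of the last IMP dose + 14 if the last cycle is a Q2W cycle or date of death + 1, whichever is earlier".
- Planned dose intensity (PDI): the planned dose "multiplied by the theoretical total number of doses started and divided by the theoretical cycle duration expressed in weeks", with four weeks allotted to each cycle started.
- RDI: 100 × ADI / PDI.

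On dose modifications, the same section states: "Dose omission is defined as a dose not administered at the scheduled visit but administered afterwards". SAP 4.7.1.1 separately defines a delayed dose as one given at least 2 days late (weekly dosing) or at least 3 days late (two-weekly dosing). Protocol 6.6.1 lists cycle delay, dose delay and dose omission as distinct actions. Protocol 6.6.2 lets an infusion be omitted when the participant has not recovered within a set number of days.

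**The concern.** RDI is a ratio of two rates, so both rates should refer to the same stretch of treatment. Here the actual rate stops its clock shortly after the last dose given, while the planned rate runs to the end of the last cycle started. Doses lost at the end shorten the actual period along with the cumulative dose, so the ratio does not register them. In a two-weekly cycle cut short, it rises above 100% with no overdose.

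The omission sentence has a different fault. A dose given after its scheduled visit is late, and the SAP already has a category for that. An infusion that is never given meets neither definition as worded.

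At stake is how tolerability reads in the exposure tables. RDI is the only relative-exposure percentage listed in SAP 4.7.1.2. It can exceed 100% for a participant who falls below the 75% share of planned cumulative doses needed for the Efficacy-evaluable population.

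**Working it through.** **Inputs.** Protocol 6.1 implies doses on study days 1, 8, 15, 22 (Cycle 1), 29, 43 (Cycle 2) and 57, 71 (Cycle 3): 8 doses over 12 weeks. The dose is 10 mg/kg; at 5 mg/kg the percentages are identical because the dose cancels.

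**Formulas (SAP 4.7.1.2).** Exposure in weeks = (day of last dose + 7 or 14 − 1)/7. ADI = cumulative dose / exposure. PDI = 10 × planned doses in started cycles / (4 × cycles started). RDI = 100 × ADI/PDI. The SAP states no RDI figure to reproduce; the check is that a full on-time course returns 100%, which it does (last row).

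**Stopping early, all earlier doses on schedule and no death during the exposure period.** C2D1 means Cycle 2 Day 1, and so on.

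| Last dose | Doses | Exposure (weeks) | ADI | PDI | RDI | Share of 8 doses |
|---|---|---|---|---|---|---|
| C1D1 | 1 | 1 | 10/1 = 10 | 40/4 = 10 | 100% | 12.5% |
| C1D8 | 2 | 2 | 20/2 = 10 | 10 | 100% | 25% |
| C1D15 | 3 | 3 | 30/3 = 10 | 10 | 100% | 37.5% |
| C1D22 | 4 | 4 | 40/4 = 10 | 10 | 100% | 50% |
| C2D1 | 5 | (29+14−1)/7 = 6 | 50/6 = 8.33 | 60/8 = 7.5 | 111% | 62.5% |
| C2D15 | 6 | 8 | 60/8 = 7.5 | 7.5 | 100% | 75% |
| C3D1 | 7 | (57+14−1)/7 = 10 | 70/10 = 7.0 | 80/12 = 6.67 | 105% | 87.5% |
| C3D15 (full course) | 8 | 12 | 80/12 = 6.67 | 6.67 | 100% | 100% |

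A participant who misses only the last dose scores 105%, above one who completes the course.

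**Where RDI does respond.**

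- One skipped dose, course otherwise completed: (70/12)/(80/12) = 87.5%.
- C1D15 skipped, then stop after C1D22: (30/4)/10 = 75%.
- C1D8 skipped, then stop after C2D1: (40/6)/7.5 = 88.9%.
- C1D8 given one day late, then stop: 20/(15/7) = 9.33, against 10, so 93.3%.
- Full course with Cycle 2 started 14 days late: (80/14)/(80/12) = 85.7%.

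**Ambiguity in PDI.** The table counts planned doses in started cycles. If the SAP's *doses started* meant doses actually given, one dose would give 10/(10/4) = 400% and seven doses 7.0/(70/12) = 120%.

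**Omission, set side by side.** Take C2D15. If it is given 4 days late, it is a delayed dose under SAP 4.7.1.1 and, read literally, also an omission under SAP 4.7.1.2. If it is skipped and never given, Protocol 6.6.2 calls it omitted. The SAP counts it as neither, because both definitions require that the dose was eventually given.

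**The case against.** Dose intensity is a rate while on treatment, and completion is a different quantity. One weekly dose followed by a 7-day tail is 10 mg/kg per week against a planned 10, so 100% is defensible as a rate. That argument stands for stops after 1 to 4 or 6 doses. There the remedy is to show completion beside RDI, since RDI alone cannot convey it. It does not explain 111% and 105%, which arise only because the two periods differ.

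Early stopping is also not hidden. SAP 4.7.1.2 summarizes number of doses, cycles started, duration and cumulative dose. SAP 4.2 reports non-completers with the main reason, and SAP 4.7.2 tabulates adverse events leading to discontinuation. This stands and limits the consequence.

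The omission sentence may have been meant as a skipped dose with treatment resumed later. That would count mid-course skips, but not a skipped C3D15, after which no dose is scheduled. The wording needs correcting on either reading.

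A reader might infer that RDI is at least 100% for every early stopper, or that the SAP misstates missed doses generally. The documents do not support this: an earlier skip brings RDI below 100%, and lateness can do so too, as shown above. A reader might also infer that the populations or the Phase 2 dose decision are compromised. They are not. SAP 3 and Protocol 9.3 define populations by share of planned doses, and Protocol 4.1 rests the dose decision on the totality of safety findings; neither cites RDI or omission counts.

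**Conclusion.** Both rules are wrong as written, and the consequence is minor. RDI does not fall for final doses lost by on-schedule early stopping, and overstates intensity at two stopping points: 111% after C2D1 and 105% after C3D1. These figures assume planned doses in started cycles as the PDI count, no earlier skip or lateness, and no death shortening the exposure period. The omission definition, taken literally, counts late doses, duplicates dose delay and leaves out skipped infusions. The errors affect the RDI summary and the participant-level and cycle-level omission rows, and possibly the rows for any dose modification. The primary response-rate analysis does not use either quantity.

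**What to change.** 1. Add percent of planned cumulative dose: out of 8 doses for the course and out of 4 for Cycle 1. The populations already use this metric. It shows 50% and 75% for stops after 4 and 6 doses, where RDI will still read 100%.
2. Keep PDI as planned doses in started cycles over four weeks per cycle started, and state that *doses started* means planned doses in started cycles.
3. Compute ADI over four weeks per cycle started plus actual delay, counting each late day once. Add the delay to ADI only; adding it to both rates would cancel it and return 100% for a full course with a 14-day cycle delay. Under this rule, stopping after C2D1 gives (50/8)/7.5 = 83.3%, stopping after C3D1 gives (70/12)/6.67 = 87.5%, and the 14-day delay still gives 85.7%.
4. Define omission, in line with Protocol 6.6.1 and 6.6.2, as a scheduled dose within a started cycle that was not given and not made up. Leave doses after definitive discontinuation to the disposition table.

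The cost is SAP wording and table programming. No new data collection is needed, because the proposed measures use the dosing dates and amounts that the SAP's existing derivations already require.

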4.7.2 Adverse events

General common rules for adverse events

All AEs will be graded according to National cancer institute common terminology for adverse events [(NCI-CTCAE) version 5.0] and coded to a lower-level term (LLT), preferred term (PT), high-level term (HLT), high-level group term (HLGT), and associated primary system organ class (SOC) using the Medical Dictionary for Regulatory Activities (MedDRA) version currently in effect at Sanofi at the time of database lock.

The AEs will be analyzed in the following 3 categories:

- Pre-treatment AEs: AEs that developed, worsened or became serious during the pre-treatment period.
- Treatment-emergent adverse events (TEAE)s: AEs that developed, worsened or became serious during the on-treatment period
- Post-treatment AEs: AEs that developed, worsened or became serious during the post-treatment period

Similarly, deaths will be analyzed in the pre-treatment, treatment-emergent and post-treatment periods.

The primary focus of AE reporting will be on TEAEs. Pre-treatment and post-treatment AEs will be described separately.

An AE with incomplete or missing date/time of onset (occurrence, worsening, or becoming serious) will be classified as a TEAE unless there is definitive information to determine it is a pre-treatment or a post-treatment AE.

If the assessment of the relationship to IMP is missing for an AE, this AE will be assumed as related to IMP. If the toxicity grade is missing for 1 of the treatment-emergent occurrences of an AE, the toxicity grade will be imputed with the maximal severity of the other occurrences. If the severity is missing for all the occurrences, the toxicity grade will be left as missing.

Multiple occurrences of the same event in the same participant will be counted only once in the tables within a treatment phase, using the maximum (worst) grade by treatment phase. Summaries will be provided for all grades combined and for grade ≥ 3 (including Grade 5). Missing grades, if any, will be included in the “all grades” category.

The AE tables will be sorted as indicated in [Table 5](#).

Table 5 - Sorting of AE tables

AE presentation	Sorting rules
SOC and PT	By the internationally agreed SOC order and decreasing frequency of PTs ^{a, b}
PT	By decreasing frequency of PTs ^a

a Sorting will be based on the overall incidence.

b The table of all TEAEs presented by SOC and PT will define the presentation order for all other tables (eg, treatment-emergent SAE) presented by SOC and PT, unless otherwise specified.

Analysis of all adverse events

The overview of TEAE with the details below will be generated:

- Any TEAE (any grade)
- Any grade ≥ 3 TEAE
- Grade 5 TEAE (any TEAE with a fatal outcome during the treatment-emergent period)
- Any TE SAE (any grade)
- Any serious, treatment-related, TE SAE (any grade)
- Any TEAE leading to definitive study treatment discontinuation
- Any TE AESI
- Any TE AESI grade ≥ 3
- Any treatment-related TEAE (any grade)
- Any grade ≥ 3 treatment-related TEAE

The AE summaries of [Table 6](#) will be generated with number (%) of participants experiencing at least one event. The analyses will be performed for all grades combined and for grades ≥ 3 .

Table 6 - Analyses of adverse events

Type of AE	MedDRA levels
All TEAE	Primary SOC and PT
	Primary SOC
	PT
TEAE related to IMP treatment as per Investigator's judgment	Primary SOC and PT
Treatment-emergent SAE	Primary SOC and PT
Treatment-emergent SAE related to IMP treatment as per Investigator's judgment	Primary SOC and PT
TEAE leading to definitive study treatment discontinuation	Primary SOC and PT
TEAE leading to death (death as an outcome of the AE as reported by the Investigator in the AE page)	Primary SOC and PT
	Primary SOC and PT
Pretreatment AEs & SAEs	Overview ^a
	Primary SOC and PT
Post-treatment AEs & SAEs	Overview ^a
	Primary SOC and PT
TEAE leading to dose reduction	Primary SOC and PT
TEAE leading to dose interruption	Primary SOC and PT

a Will include the following AE categories: any AEs, any SAEs, any AEs leading to death, any AEs leading to permanent intervention discontinuation

Analysis of deaths

In addition to the analyses of deaths included in [Table 6](#) the number (%) of participants in the following categories will be provided:

- Deaths during the treatment-emergent and post-treatment periods by reason for death
- An overview of Grade 5 AEs will be provided with the following categories:
 - Grade 5 AE (TEAE and post-treatment).
 - Fatal TEAE (regardless of date of death/period).
 - Grade 5 TEAE with a fatal outcome during the treatment period,
 - Any Grade TEAE with a fatal outcome during the post-treatment period.
 - Post-treatment Grade 5 AE (excluding a TEAE that worsened to Grade 5 during the post-treatment period).
- Deaths in enrolled but not treated participants

Analysis of infusion reactions (IRs) classified as an AESI

IR analysis will include all adverse events regardless of relationship to isatuximab. The IRs will be summarized as follow:

- Number (%) of participants experiencing IRs according to investigator reported AEs presented by primary SOC and PT will be summarized by grade.
- Description of the IR diagnoses (using the diagnosis reported and excluding symptoms).
 - Number (%) of participants' action taken,
 - Number (%) of participants with only 1, ≥ 1 , ≥ 2 , ≥ 3 , ≥ 4 and ≥ 5 episodes,
 - Number (%) of participants with first occurrence of IR at the first infusion and subsequent infusions,
 - Number (%) of participants with IR at the first and subsequent infusions,
 - Number (%) of participants with at least two episodes of IRs at the same infusion,
 - Day of onset from infusion,
 - Duration (in days).
- Number of participants with symptoms of IRs (as reported by investigator) by SOC and PT.

Analysis of other adverse events of special interest (AESIs)

Other adverse events of special interest (AESIs) will be selected for analyses as indicated in [Table 7](#). Number (%) of participants experiencing at least one event will be provided for each event of interest. Tables will be sorted as indicated in [Table 5](#).

Table 7 - Selections for other AESIs

AESIs	Selection
Symptomatic overdose	e-CRF specific tick box on the AE page
Pregnancy	e-CRF specific tick box on the AE page

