6.6 DOSE MODIFICATION

6.6.1 General rules

Cycle delay (ie, delay of IMP for Cycle 2 and 3), dose delay, or dose omission (ie, omission within a cycle) are permitted in case of toxicity.

Administration of the IMP will be discontinued in the event of a TEAE that persists despite appropriate dose modifications or any other AE that, in the opinion of the Investigator, warrants discontinuation.

There will be no dose reduction for isatuximab.

Any changes to IMP administration must be recorded in the eCRF.

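### SAP Table 6 tabulates adverse events leading to dose reduction, which the protocol rules out, but not those leading to delay or omission, which it permits; the SAP Table 4 rule can also count an incomplete infusion as a reduction

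*SAP*

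**What the plan says.** Protocol 6.6.1 sets the dosing actions. For toxicity, cycle delay is allowed, and so are the others: "dose delay, or dose omission (ie, omission within a cycle) are permitted in case of toxicity". It then states "There will be no dose reduction for isatuximab". Protocol 6.6.3, Table 5 directs delay for a range of hematological and non-hematological events, and Protocol 6.6.4 provides for stopping and restarting an infusion after a reaction.

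SAP 4.7.2, Table 6 has rows for definitive discontinuation, for "TEAE leading to dose reduction" and for "TEAE leading to dose interruption". It has none for delay or omission.

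The SAP defines interruption of a dose in one place only, 4.7.1.2, as follows: "A dose will be considered as interrupted if the IMP administration is stopped during an infusion regardless of whether it is restarted or not". The same section sets the reduction rule: "If the current dose level is below the dose level interval of the previous dose administration, then the current dose level is considered reduced". The intervals are in SAP Table 4: above 7.5 mg/kg for the 10 mg/kg level, and above 0 up to 7.5 mg/kg for the 5 mg/kg level. The first infusion is exempt: "The first IMP administration will not be counted as a dose reduction". Actual dose "is defined as the actual dose (mg) administered divided by the body weight at the time".

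**The concern.** The AE tables by dosing action do not match the actions the protocol uses. One table is reserved for an action that should not occur, while the main planned responses to toxicity, holding or skipping a dose, have none.

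Tolerability is the Phase 1 primary objective and safety is a Phase 2 secondary objective. Pre-defined unacceptable toxicity covers only Grade 4 findings in Cycle 1, so lower-grade events that cause doses to be held are an important part of the remaining tolerability picture. Missed doses also decide who is safety evaluable, efficacy evaluable or replaceable. A reader of the report would see how many doses were delayed or omitted, but no summary of which events caused it.

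The reduction rule raises a second, separate problem. It may label an infusion that was cut short as a dose reduction, an action nobody prescribed.

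**Working it through.** **1. Actions set side by side.** No power or alpha figure is involved. The check compares Protocol 6.6 with SAP 4.7.1 and SAP Table 6.

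| Action | Protocol | Counted as exposure in SAP 4.7.1 | AE row in SAP Table 6 |
|---|---|---|---|
| Cycle delay | permitted (6.6.1) | yes, banded 3 to 7, 8 to 14 and over 14 days | none |
| Dose delay | permitted (6.6.1) | yes | none |
| Dose omission | permitted (6.6.1) | yes | none |
| Stop within an infusion | provided for (6.6.4) | yes | yes |
| Dose reduction | ruled out (6.6.1) | yes, by the Table 4 rule | yes |

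The three actions named in 6.6.1 have exposure counts and no AE row. The one that 6.6.1 rules out has both.

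**2. The reduction rule.** Let d(k) be the dose given at infusion k, in mg/kg. The column heading in SAP Table 4 (Actual dose level) and its lower bound of above 0 both suggest that this is what dose level means, though the SAP does not say so outright. Infusion k (k of 2 or more) is flagged if d(k) lies below the interval containing d(k-1).

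- If d(k-1) is above 7.5, the flag is raised when d(k) is 7.5 or less. At 10 mg/kg that is 7.5/10 = 75% delivered or less.
- If d(k-1) is above 0 and at most 7.5, a flag would need d(k) of 0 or less, so no infusion actually given is flagged.

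The plan has 4 + 2 + 2 = 8 infusions. Applied to illustrative sequences, with all other infusions given in full:

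| Level | Incomplete infusion(s) | Flagged as reduced |
|---|---|---|
| 10 mg/kg | 2nd, 5 mg/kg given | 2nd |
| 10 mg/kg | 2nd, 7.5 mg/kg given | 2nd |
| 10 mg/kg | 2nd, 7.6 mg/kg given | none |
| 10 mg/kg | 2nd and 3rd, 5 mg/kg each | 2nd only |
| 10 mg/kg | 1st, 5 mg/kg given | none |
| 10 mg/kg | 1st and 2nd, 5 mg/kg each | none |
| 5 mg/kg | 2nd, 2.5 or 0.5 mg/kg given | none |

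No row contains a prescribed reduction, yet three rows produce a flag. The third and fourth rows also show that the flag does not track under-delivery consistently.

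**3. Omission.** Protocol 6.6.1 treats omission as a dose left out within a cycle. SAP 4.7.1.2 defines it as a dose missed at its scheduled visit and given later, which is closer to a delay. A new AE row that used the term without settling this would overlap with delay.

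**4. Why missed doses matter here.** Assume omitted doses are not made up. One omission in Cycle 1 leaves 3/4 = 75% of that cycle's doses, below the 90% needed for the Safety Evaluable population. Over the full course, two omissions leave 6/8 = 75%, which still meets the 75% efficacy-evaluable threshold; three leave 5/8 = 62.5%, which does not.

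**The case against.** Much can be said for the plan as it stands. Four points narrow what can be claimed.

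- A reader might infer that events causing delays or omissions appear in no AE table or cannot be identified. The documents do not support that. The events are in the all-TEAE tables by SOC and PT, and Phase 1 events are listed. Action taken is tabulated for infusion reactions in SAP 4.7.2. Protocol 6.6.2 requires the reason for a dose delay. What is missing is a planned summary that joins event to action.
- A reader might infer that the Table 4 rule fills the Table 6 reduction row. The SAP does not say so. The rule sits in the exposure section, and the AE row could rest on the investigator's recorded action. The mislabelling is therefore established, conditionally, only for the exposure count.
- A reader might treat the absence of flags at the first infusion, or at 5 mg/kg, as a defect. If no reduction is prescribed, zero is the correct count. Stops at the first infusion are still captured as interruptions and in the infusion-reaction analysis.
- A reader might expect an empty reduction table to be taken as evidence of good tolerability. That is conjecture. The row could serve as a deviation check, though the SAP does not describe it as one.

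The word interruption is also used for gaps between doses: in Protocol Table 5, and in the replacement rule that the SAP repeats. The interruption row might have been meant to include dose holds. That shows ambiguity, and the SAP's own definition points the other way. Finally, Protocol 9.4.2 asks for no AE table by reduction, delay or omission, so no protocol-required analysis is missing. These objections limit the point but leave the mismatch in Table 6 standing.

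**Conclusion.** The point holds in a limited form. Table 6 gives a row to an action the protocol rules out and none to the three modifications that 6.6.1 permits for toxicity. The interruption row does not clearly fill that gap.

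The Table 4 finding is conditional. It needs the 10 mg/kg level, the second infusion or later, a previous dose above 7.5 mg/kg, no more than 75% delivered, and dose level read as dose given. The documents give no frequency for such infusions. It may be low, because Protocol 6.6.4 allows an interrupted infusion to be restarted and the remaining dose to be given the same day. Under-delivery would in any case show in cumulative dose and relative dose intensity.

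Only descriptive tolerability reporting is affected. The response-rate analysis and the definitions of the analysis populations do not change.

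**What to change.** Amend the SAP as follows.

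1. In Table 6, replace the reduction row with TEAEs leading to dose delay, cycle delay or dose omission, by SOC and PT. State that the interruption row means stops within an infusion.
2. In 4.7.1.2, drop the Table 4 reduction rule or base it on the prescribed dose. Report incomplete infusions as percent of planned dose delivered, for each infusion and dose level.
3. Reconcile the SAP definition of omission with Protocol 6.6.1 before the new row is programmed, so that delay and omission do not overlap.
4. State whether the Table 6 rows by dosing action use the investigator's recorded action or a derived variable.

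The cost is SAP wording and one more AE table. Protocol 6.6.1 requires changes in IMP administration to be recorded in the eCRF, and 6.6.2 requires the reason for a dose delay. Neither shows that the specific adverse event is linked to a delay or omission, so that link needs to be confirmed against the eCRF.
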